11.4 Documented cardiovascular event (myocardial infarction or ischemic stroke)

Patients meet the cardiovascular event outcome if they have a clinically diagnosed acute myocardial infarction or ischemic stroke between randomization and hospital discharge. A clinical diagnosis of acute myocardial infarction must be accompanied by elevation of the local cardiac troponin assay to greater than 3-times the upper limit of normal. A clinical diagnosis of acute ischemic stroke must be accompanied by imaging confirmation.

11.5 Transfusion reaction

Patients meeting any of the following within 6 hours of initiation of the study product infusion will be classified as experiencing symptoms consistent with a transfusion reaction:

- New increase in body temperature, defined as temperature >38.0 C (100.4 F) or increase in temperature by >1 C (1.8 F) compared to temperature at the beginning of the infusion

- Decline in oxygen saturation, defined as an absolute drop in SpO₂ by more than 4% or increase in supplemental oxygen to prevent an absolute drop in SpO₂ by more than 4%
- New hives
- New rash (other than hives)
- New itching
- Chest imaging, such as a chest x-ray, demonstrating new or worsening pulmonary edema, pulmonary infiltrates, or effusion
- Clinically diagnosed anaphylaxis

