5.6 Criteria for Stopping Study Infusion

Infusion of study treatment will be halted if any of the following manifestations of transfusion reaction develop fever, rash, diffuse itching, acute increase in heart rate by greater than 20 beats per minute. If any of these symptoms develop, the patient will be evaluated by a clinician or study team member. Study treatment will be held until resolution of the symptoms. Study treatment will be restarted one time, but if symptoms recur, study treatment will be discontinued and not restarted. If the patient has recurrent symptoms on restarting study treatment, the blood bank will be notified to evaluate for potential transfusion reaction. If there is significant concern that the symptoms, beyond rash or itching, are secondary to the infusion, then infusion will not be restarted, and the patient will be evaluated for transfusion reaction.

In addition, the infusion will be stopped and not restarted if the patient develops any of the following signs or symptoms of anaphylaxis: hives; pruritus; flushing; swollen lips, tongue or uvula; worsening of shortness of breath; wheezing; stridor; hypoxemia; a decrease in systolic blood pressure to less than 90 mmHg or greater than 30% decrease from baseline or a diastolic drop of greater than 30% from baseline; bradycardia less than 40 beats per minute that is associated with dizziness, nausea or feeling faint; any other symptom or sign which

in the good clinical judgment of the study clinician or supervising provider warrants halting the infusion. For example, the rapid onset of gastrointestinal symptoms, such as nausea, vomiting, diarrhea, and cramps, may be manifestations of anaphylaxis and may warrant an immediate halt prior to meeting full severe adverse event (SAE) criteria.

Any suspected reactions related to study product that result in stopping of study transfusion must be reported as an adverse event.

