12.3 Safety Monitoring

Assuring patient safety is an essential component of this protocol. Each participating investigator has primary responsibility for the safety of the individual participants under his or her care. The investigators will determine daily if any adverse events occur during the period from enrollment through **study day 4,(which is** 72 hours after completion of the study product infusion, or hospital discharge, whichever occurs first, and will determine if adverse events are related to study procedures. Adverse events are not required to be reported to the IRB unless the investigator feels the adverse event **was related** to study infusion or study procedures.

The following adverse events will be collected in the adverse event case report forms:

- Serious adverse events (as defined in protocol section 12.2 of this protocol) that are study related (or of uncertain relationship) or occur within 72 hours of the study infusion
- Non-serious adverse events that are study procedures or of uncertain relationship
- Events leading to permanent discontinuation of study infusion (which, by definition, are study related)

The protocol for reporting adverse events in the trial's electronic data capture system are summarized in Table 4.

Table 4. Protocol for reporting adverse events

Type of Adverse Event	Time for Recording in the EDC
Serious, study related	24 hours
Serious, not study related and within 72 hours of infusion	72 hours
Serious, not study related and after 72 hours following	Recording in the EDC is not required
Not serious, study related	72 hours
Not serious, not study related	Recording in the EDC is not required

Study-specific clinical outcomes (Primary, Secondary and Safety Outcomes and Assessments During the Study), including serious outcomes such as organ failures and death, are systematically recorded in the case report forms and are exempt from adverse event reporting unless the investigator deems the event to be related to the administration of study plasma or the conduct of study procedures (or of uncertain relationship).

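### SAP 11.5 can score an infusion permanently stopped under Protocol 5.6 for an isolated blood-pressure, heart-rate, swelling, wheeze or stridor sign as no transfusion reaction, unless anaphylaxis is diagnosed or another listed item occurs

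*SAP*

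**What the plan says.** Protocol 6 leaves outcome definitions to the SAP, so SAP 11.5 controls how a transfusion reaction is scored. Patients with at least one of seven findings "within 6 hours of initiation of the study product infusion will be classified as experiencing symptoms consistent with a transfusion reaction". The seven are a temperature rise, a fall in oxygenation ("Decline in oxygen saturation, defined as an absolute drop in" SpO2 of more than 4%, or extra oxygen given to prevent that drop), hives, other rash, itching, new or worse chest imaging, and "Clinically diagnosed anaphylaxis". The last item has no criteria and no reference to Protocol 5.6. SAP 7 analyses the outcome as an unadjusted risk difference.

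Protocol 5.6 names two sets of signs.
- The first set leads to a halt, with one restart allowed. It reads "manifestations of transfusion reaction develop fever, rash, diffuse itching, acute increase in heart rate by greater than 20 beats per minute".
- For the second set, "the infusion will be stopped and not restarted if the patient develops any of the following signs or symptoms of anaphylaxis". That list runs "hives; pruritus; flushing; swollen lips, tongue or uvula; worsening of shortness of breath; wheezing; stridor; hypoxemia", then "a decrease in systolic blood pressure to less than 90 mmHg or greater than 30% decrease from baseline" or a comparable diastolic fall, then symptomatic bradycardia, then a catch-all for clinical judgement.

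Protocol 5.6 also requires that suspected reactions which stop the infusion be reported as adverse events. Protocol 12.3 collects "Events leading to permanent discontinuation of study infusion (which, by definition, are study related") on the adverse event form. Protocol 6.3 and Table 3 in Protocol 8.7 give the outcome the parenthetical label fever/rash, which the SAP drops.

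**The concern.** The two documents describe the same clinical event with different sign lists. Protocol 5.6 treats an acute heart-rate rise as a transfusion reaction, and treats hypotension, swelling and airway signs as anaphylaxis. The SAP outcome names none of these, so a patient can lose the rest of the infusion because of a suspected reaction and still be coded as having had none.

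This row matters because it is the only planned comparison of acute infusion reactions that rests mainly on observed signs. TRALI, TACO and transfusion-related infection (SAP 11.6 to 11.8) each require a clinical diagnosis. If haemodynamic and airway reactions enter the row only through an undefined diagnostic label, its content depends on how clinicians word their notes. Protocol 4.7 states that the staff who administer the product are not blinded.

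**Working it through.** The documents give no expected reaction rate, and the plan states no figure to reproduce. The check is a side-by-side reading.

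**1. Match each sign in Protocol 5.6 to an item in SAP 11.5.**

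| Protocol 5.6 set | Named signs | Own item in SAP 11.5 | No item of its own |
|---|---|---|---|
| Reaction (halt, one restart) | 4 | 3: fever, rash, itching | 1: heart-rate rise |
| Anaphylaxis (permanent stop) | 10, before the catch-all | 3: hives, pruritus, hypoxemia (through the SpO2 item, with its own 4% threshold) | 7: flushing, swelling, worse shortness of breath, wheeze, stridor, blood-pressure fall, symptomatic bradycardia |
| Total | 14 | 6 | 8 |

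Counting the systolic and diastolic falls separately gives 9 of 15. Coding flushing as rash lowers either count by one, to 7 of 14 or 8 of 15.

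**2. Score two hypothetical records literally.**

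- *Record A.* Systolic pressure falls from 130 to 80 mmHg with wheeze 30 minutes into the infusion; temperature and SpO2 are unchanged. The fall is 50/130 = 38% and the value is below 90, so 5.6 stops the infusion for good. In SAP 11.5 this is a reaction if someone diagnoses anaphylaxis, or if another listed item appears within 6 hours of the start. Otherwise it is not.
- *Record B.* Heart rate rises by 35 beats per minute. The infusion is held and restarted, the rise recurs, and the infusion is discontinued. A heart-rate rise is not among the signs that 5.6 calls anaphylaxis, so linking the anaphylaxis item to that list would not capture it. SAP 11.5 scores no reaction unless anaphylaxis is diagnosed on other grounds or another listed item occurs.

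**3. See where else such events appear.** Protocol 5.6 and 12.3 put both stops on the adverse event form. SAP 7 reports adverse events by assigned arm, and SAP 2 describes them by arm at each of the three interim analyses. The stops are therefore visible, but outside the transfusion-reaction risk difference.

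This backstop has a limit. The recommended infusion lasts about 1 to 3 hours (Protocol 5.1), whereas the outcome window is 6 hours. A sign that appears after the infusion has ended stops nothing. If it is not serious, Protocol 12.3 collects it only when it is judged related or of uncertain relationship.

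**4. Ask which way the risk difference would move.** Let u be the proportion of patients in an arm with an unscored event. The reported difference equals the full difference minus (u plasma − u placebo). Purely as an assumption, take u = 0.5% to 2% for plasma and 0% to 1% for placebo, with 500 patients per arm and no capture through any other item. That is 2.5 to 10 plasma events and 0 to 5 placebo events. The four corners are:

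- 0.5 − 0 = +0.5 points
- 2 − 0 = +2 points
- 2 − 1 = +1 point
- 0.5 − 1 = −0.5 points

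A positive value means the reported difference is too low; a negative value means it is too high. The sign changes within the assumed range. With equal u in both arms, event counts fall but the difference is unaffected.

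**The case against.** The strongest reply has four parts.

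- **The anaphylaxis item.** Hypotension and wheeze are on the list that 5.6 calls signs of anaphylaxis, so many such patients would be diagnosed and scored. Wheeze with desaturation or added oxygen also scores through the SpO2 item. This stands, and it means airway coverage is partial rather than absent. A reader might infer that every infusion stopped for hypotension or wheeze is scored as no reaction. The documents do not support that; it happens only when neither route applies.
- **Adverse event reporting.** A reader might also infer that these events vanish or survive only as individual reports. They do not, because they are described by arm for the DSMB and at the end. This stands and confines the gap to one row.
- **A stopping rule is not an outcome definition.** Protocol 5.6 is precautionary and has a catch-all, nothing obliges the SAP to mirror it, and the SAP list is already broader than fever/rash. This is fair as far as copying every sign goes. It does not explain why a permanent stop for a suspected reaction, which Protocol 12.3 treats as study related by definition, should count as no reaction.
- **Data availability.** Infusion monitoring follows site policy (Protocol 5.5), and Appendix A schedules vital signs only at baseline and daily while the patient is hospitalised. Blood pressure across the 6 hours may not be in the database. This stands, so the remedy should rest first on data already collected.

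**Conclusion.** The mismatch is real and limited. SAP 11.5 has no item for blood-pressure fall, heart-rate change, swelling, wheeze or stridor, and it does not say whether clinically diagnosed anaphylaxis covers the 5.6 signs. An infusion permanently stopped for one of these alone can be coded as no transfusion reaction.

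It is tempting to conclude that the plasma-versus-placebo difference is understated. The documents do not establish that: they give no rates, and step 4 shows that the direction depends on which arm has more unscored events. What can be said is that the row can misclassify an event the protocol itself treats as a suspected reaction. This assumes that SAP 11.5 is applied literally and that no case report form instruction, which the documents do not show, supplies the missing link.

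**What to change.** Reconcile Protocol 5.6, the fever/rash label in Protocol 6.3 and 8.7, and SAP 11.5. In SAP 11.5:

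1. Count as a transfusion reaction any permanent discontinuation of the study infusion for a suspected reaction within the 6-hour window, taken from the adverse event form. This would capture Records A and B.
2. State that the anaphylaxis item includes the signs Protocol 5.6 lists as anaphylaxis, where they are recorded: for example a blood-pressure fall at the thresholds already written there, wheeze, stridor or swelling.
3. Report the risk difference for the composite and for each component, by arm.

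The cost is mainly SAP wording and one table, since discontinuations are already collected. New vital-sign fields are optional and depend on what the infusion form captures. There are two drawbacks. Some background hypotension or respiratory worsening will be counted in both arms, and the discontinuation component depends on unblinded administering staff. The per-component table makes both visible. Protocol 5.6 is unchanged as a clinical rule.

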4. STUDY POPULATION AND ENROLLMENT

4.1 Inclusion Criteria

1. Age greater than or equal to 18 years
2. Currently hospitalized or in an emergency department with anticipated hospitalization.
3. Symptoms of acute respiratory infection, defined as one or more of the following:
 - a. cough
 - b. Chills, or a fever (greater than 37.5° C or 99.5° F)
 - c. shortness of breath, operationalized as a patient having any of the following:
 - i. Subjective shortness of breath reported by a patient or surrogate.
 - ii. Tachypnea with respiratory rate greater than 22 breaths per minute.
 - iii. Hypoxemia, defined as SpO₂ less than 92% on room air, new receipt of supplemental oxygen to maintain SpO₂ greater than or equal to 92%, or increased supplemental oxygen to maintain SpO₂ greater than or equal to 92% for a patient on chronic oxygen therapy
4. Laboratory-confirmed SARS-CoV-2 infection within the past 14 days.

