8.7 Safety Outcomes and Adverse Events

The frequency and description of safety outcomes and adverse events will be reported. The association between intervention group and safety outcomes will be estimated without covariate adjustment. The following table lists the safety outcomes and the planned analyses (Table 3).

Table 3. Trial safety outcomes.		
Outcome	Type	Analysis
Receipt of renal replacement therapy	Binary	Risk difference
Documented venous thromboembolic disease (DVT or PE)	Binary	Risk difference
Documented cardiovascular event (myocardial infarction or ischemic stroke)	Binary	Risk difference
Transfusion reaction (fever/rash)	Binary	Risk difference
Transfusion related acute lung injury (TRALI)	Binary	Risk difference
Transfusion associated circulatory overload (TACO)	Binary	Risk difference
Transfusion related infection	Binary	Risk difference

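### SAP 11.5: the >38.0 C limb of the transfusion-reaction outcome does not require the fever to be new, and the composite is wider than the protocol's fever/rash label

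*SAP*

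**What the plan says.** SAP 11.5 lists seven items. A patient who meets any one of them "within 6 hours of initiation of the study product infusion will be classified as experiencing symptoms consistent with a transfusion reaction".

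- **Temperature:** "New increase in body temperature, defined as temperature >38.0 C (100.4 F) or increase in temperature by >1 C". The text then adds a reference point, "compared to temperature at the beginning of the infusion", which follows directly on the rise limb.
- **Oxygenation:** an absolute fall in SpO₂ of more than 4%, "or increase in supplemental oxygen to prevent an absolute drop in" SpO₂ of that size.
- **Imaging:** "Chest imaging, such as a chest x-ray, demonstrating new or worsening pulmonary edema, pulmonary infiltrates, or effusion".
- **Remaining items:** new hives, other new rash, new itching, and clinically diagnosed anaphylaxis.

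Protocol sections 2, 6.3 and 8.7 (Table 3) carry the same outcome as "Transfusion reaction (fever/rash"). The SAP outcome list and the table in SAP section 7 drop the parenthesis. Protocol section 6 defers outcome definitions to the SAP.

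Both documents analyse the outcome as an unadjusted risk difference between arms. Neither gives an expected rate, alpha, margin or power for it.

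On eligibility, one qualifying symptom in Protocol 4.1 is "Chills, or a fever (greater than 37.5° C or 99.5° F"), and hypoxemia is another. Nothing in Protocol 4.2 excludes patients who are febrile.

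**The concern.** The heading of the temperature item promises a new event, but the first half of its definition tests only the level reached. A patient at 38.6 C before the infusion who stays there, or cools to 38.2 C, satisfies that half. Two programmers could code the outcome differently and each point to the text.

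The oxygenation and imaging items raise a related question. Protocol 6.4 ties most COVID-19 morbidity to hypoxemia, so the disease itself can trigger these items within six hours, and neither needs a judgement that the infusion was responsible. A results row carrying the protocol's label would therefore report more than fever and rash.

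What is at stake is the clarity and precision of one safety comparison. Events unrelated to plasma occur in both arms and make a true excess harder to see.

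**Working it through.** **Step 1. The temperature rule under each reading.** The temperatures are illustrative.

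| Start | Highest within 6 h | Rise | Literal reading | >38.0 C must be new |
|---|---|---|---|---|
| 37.2 | 38.1 | 0.9 | event | event |
| 36.8 | 37.9 | 1.1 | event | event |
| 38.6 | 38.6 | 0 | event | no event |
| 38.6 | 39.7 | 1.1 | event | event |

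The readings differ only for patients who start above 38.0 C and do not rise by more than 1 C.

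**Step 2. Effect of background events on the risk difference.** The plan states no figure for this outcome, so there is none to reproduce. Inputs:

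- n = 500 per arm (SAP section 4).
- b, the background rate in both arms: assumed.
- q, the reaction risk added by plasma, independent of background: assumed.
- Two-sided alpha of 0.05: assumed. The plan specifies no test.

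Formulas:

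- Plasma-arm rate: p = b + (1 − b)q
- Risk difference: RD = p − b = (1 − b)q
- SE = √[p(1 − p)/n + b(1 − b)/n]
- Power ≈ Φ(RD/SE − 1.96); 95% half-width = 1.96 × SE

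For q = 3%, b = 10%: p = 0.10 + 0.90 × 0.03 = 0.127; RD = 0.027; SE = √[(0.1109 + 0.0900)/500] = 0.0200; RD/SE = 1.347; power = Φ(−0.613) = 0.27.

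| b | p | RD (points) | Half-width (points) | Power, q = 3% |
|---|---|---|---|---|
| 2% | 4.94% | 2.9 | 2.3 | 0.72 |
| 10% | 12.7% | 2.7 | 3.9 | 0.27 |
| 20% | 22.4% | 2.4 | 5.1 | 0.15 |
| 30% | 32.1% | 2.1 | 5.7 | 0.11 |

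**Step 3. Other assumed effects.** Here and in step 4 a pooled standard error is used under the null; the unpooled form agrees to within about 0.002.

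- q = 5%: power 0.97, 0.58, 0.33 and 0.22 at b = 2%, 10%, 20% and 30%.
- q = 10%: power 0.98, 0.84 and 0.65 at b = 10%, 20% and 30%.
- q = 2%: power only 0.61 even at b = 1%.

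**Step 4. The already-febrile share alone.** Steps 2 and 3 vary the total background. To vary only the share f who start above 38.0 C, assume that all of them count, that the other items give 5% background, and that q = 5%. Then b = 0.05 + 0.95f.

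| f | b | RD (points) | Power |
|---|---|---|---|
| 0% | 5.0% | 4.8 | 0.82 |
| 5% | 9.8% | 4.5 | 0.59 |
| 10% | 14.5% | 4.3 | 0.44 |
| 20% | 24.0% | 3.8 | 0.28 |
| 30% | 33.5% | 3.3 | 0.20 |

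The value of f is not in the documents.

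**The case against.** The other side has a good deal right.

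- **The wording is ambiguous rather than plainly wrong.** The item is headed as a new increase, the skin items are all qualified as new, and the start-of-infusion reference could be read to govern both limbs. This stands: the literal reading is one reading, not an established rule.
- **The wider list is authorised.** A reader might infer that the SAP improperly enlarged a protocol outcome. It did not: Protocol section 6 places the definitions in the SAP, and Protocol 5.6 already treats hypoxemia and worsening breathlessness as infusion-related signs. What remains is a label that does not match its definition.
- **A sensitive screen against randomized placebo is defensible.** Both arms face the same criteria, so background events create no false difference. TRALI, TACO and transfusion-related infection are separate outcomes that need a clinical diagnosis. Suspected reactions that stop the infusion must be reported as adverse events. This stands, and it is why the full composite should be kept.
- **The entry criterion says little about temperature at infusion.** Its cutoff is 37.5 C, fever is one of several qualifying symptoms, and onset may be up to 14 days before randomization. This also stands: febrile patients can be enrolled, but how many exceed 38.0 C at the start is unknown.
- **Power is not the plan's yardstick.** The plan estimates risk differences and names no test. The power figures are only a convenient scale for lost precision.

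A reader might also infer that COVID-19 events will swamp the plasma signal, or that this is the main comparison for the likeliest plasma harm. Neither is supported. The documents give no rates, an assumed 10% effect keeps 84% power at 20% background, and no section ranks the harms.

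**Conclusion.** The concern holds as a minor but specific definitional defect. The >38.0 C limb lacks the condition that its heading implies, so on a literal reading patients already febrile are classified as reactions in both arms. Separately, the protocol label is narrower than the SAP definition, which includes respiratory items that need no attribution to the infusion.

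The consequence is possible dilution, not bias between arms: the risk difference shrinks by (1 − b) and its interval widens. The size cannot be determined from the documents. The figures rest on assumed background rates, assumed plasma effects, independence of the two, and an assumed two-sided 5% level. The 0.72 to 0.11 range shows what total background does. It measures neither this defect alone nor what the fix would recover, because new COVID-19 fevers, desaturation and imaging changes would remain in the composite.

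**What to change.** In SAP 11.5, for outcome classification only:

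- Count a temperature above 38.0 C only when the start-of-infusion temperature was at or below 38.0 C; otherwise require a rise of more than 1 C from that value.
- Keep the full composite, and add a by-arm row for the fever, hives, rash, itching and anaphylaxis components.
- Align the protocol's label in sections 2, 6.3 and 8.7 with the SAP definition.

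The cost is one sentence of SAP wording, one extra table row and a label edit. No new data are needed, because the existing rise limb already uses the start-of-infusion temperature. The change does not touch the rules for holding or stopping an infusion.
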